16 STATISTICAL METHODS AND DATA ANALYSIS

16.1 General Design Issues

All planned analyses will be prospectively defined for this study and approved by the CC prior to unblinding of data. The statistical analysis plan (SAP) will contain detailed information regarding the data analysis. The SAP will be finalized prior to trial completion and will be approved by the coordinating center statistical team as well as the National Heart, Lung, and Blood Institute (NHLBI) program officer.

Analysis of the LIFE Study will be based on intention to treat (ITT). That is, subjects will be analyzed (and endpoints attributed) according to the treatment strategy to which subjects are randomized, regardless of subsequent additional post-randomization treatment and medical care. The ITT population will correspond to all randomized subjects.

Statistical comparisons will be performed using two-sided significance tests. Baseline demographic and clinical variables will be summarized for each randomized arm of the study. Descriptive summaries of the distribution of continuous variables will be presented in terms of percentiles (e.g., median, 25th and 75th percentiles) along with means and standard deviations. Categorical variables will be summarized in terms of frequencies and percentages.

In addition, exploratory analyses will be performed to help explain and understand findings

observed from the planned analyses. Statistical tests with a 2-sided p-value <0.05 will be considered statistically significant, unless otherwise stated. Analyses will be performed using SAS software (SAS Institute, Inc, Cary, NC).

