18 STUDY ADMINISTRATION

18.1 Data and Safety Monitoring Board

A DSMB has been appointed by the NHLBI for the HFN, and will function as the DSMB for this trial. This committee consists of a group of highly experienced individuals with extensive pertinent expertise in HF and clinical trials. The DSMB will advise the HFN Steering Committee regarding the continuing safety of current subjects and those yet to be recruited, as well as the continuing validity and scientific merit of the trial. Safety data, summarized at the treatment level, will be assessed approximately every 3 months by the DSMB. The safety analyses will be based on the entire ITT population. Safety will be evaluated by comparing the occurrence of AEs and changes in laboratory values of the active treatment arm compared to the active

control arm.

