### 2.2 Randomization

Patients are randomized in a 1:1 ratio to either LCZ696 + Valsartan-placebo or Valsartan + LCZ696-placebo. The randomization scheme consists of a permuted block design with stratification by clinical site and atrial fibrillation status.

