#### \* Analysis Modifications to Address COVID-19 Pandemic

The coronavirus COVID-19 pandemic has had a major impact on the performance of the LIFE trial. It was anticipated that patients will have greater difficulty attending study visits on their planned schedule due to restrictions on outpatient visits at many institutions. Therefore, patients will be unable to participate in study-related procedures such as biomarker sample collection, which comprises the primary endpoint for this trial. Additionally, due to restrictions on clinic access and potential concerns with patients going to the emergency department where exposure risk to COVID-19 is increased, we expect reporting of clinical endpoints such as emergency department visits and even hospital admissions to be impacted by the pandemic.

Therefore, due to the unexpected disruption brought on by the COVID-19 pandemic, the analysis plan was amended to restrict the reported program analyses to those patients that had their Week 12 visit prior to March 1, 2020, when the COVID-19 pandemic became more active in the continental United States. This translated to restricting the reported analyses to patients that were randomized on December 7, 2019 or earlier. Additionally, any study data collected after March 1, 2020 were excluded from the analyses for those patients randomized on or prior to December 7, 2019. This amended population will be labeled as the pre-COVID-19 population within the analysis plan.

The original protocol-specified analyses were to be conducted on all randomized patients using all available information. Those analyses will still be performed but will be considered to be sensitivity analyses.

Of the 365 patients randomized, 335 will be included in the pre-COVID-19 population. Twenty five of the 335 patients will have some visit information removed due to study visits occurring March 1, 2020 or later. The

remaining 30 patients will only contribute to the original protocol-specified analyses, now part of the sensitivity analyses.

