#### 4. General Methodology

Medians, 25th and 75th percentiles will be presented for continuous variables; the number and percentage of patients in each category will be presented for categorical variables. For all endpoints a p-value  $\leq 0.05$  will be considered statistically significant and all tests will be 2-sided. Analyses will be performed using validated SAS software (SAS Institute, Inc., Cary, NC). Appropriate statistical models will be used to examine the effect of treatment on both the primary, secondary, and tertiary outcomes in the study.

The modeling that will be used for each endpoint will be detailed within each endpoint description section.

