### **13. Safety analysis**

#### **13.1 – Safety Endpoint #1**

Safety Endpoint #1: Comparison of serious adverse events at the level of MedDRA preferred term, using the pre-COVID-19 population.

Response Variable Definitions: The number of patients experiencing each unique serious adverse event (SAE) type based on MedDRA preferred term within body system.

Additional Covariates: None

Handling of Dropouts and Missing Data: No adjustments for missing data will be made.

Sensitivity Analysis: Re-calculate the endpoint analysis using the original ITT population.

Statistical Tests: Fisher's mid-p will be calculated for each serious adverse event based upon the unique MedDRA preferred term within a body system.

Interpretation of Results: Lower event rates indicate a better outcome for LCZ696 arm versus Valsartan.

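### SAP 13.1 compares SAEs only term by term, with no any-SAE comparison and no statement that the term-level p-values are descriptive

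*SAP*

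**What the plan says.** SAP 13.1 contains a single safety endpoint: "Comparison of serious adverse events at the level of MedDRA preferred term, using the pre-COVID-19 population". The method is Fisher's "mid-p will be calculated for each serious adverse event based upon the unique MedDRA preferred term within a body system", repeated in the original ITT population as a sensitivity analysis. The stated interpretation is directional: "Lower event rates indicate a better outcome for LCZ696 arm versus Valsartan". The section names no comparison of patients with at least one SAE, no test at body-system level, no multiplicity rule, and no statement that the p-values are descriptive.

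SAP 4 says that, for all endpoints, a p-value of 0.05 or less "will be considered statistically significant and all tests will be 2-sided". Protocol 16.1 sets a similar default: "Statistical tests with a 2-sided p-value <0.05 will be considered statistically significant, unless otherwise stated". Nothing in SAP 13.1 states otherwise.

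Protocol 18.1 describes a broader comparison, with valsartan as the comparator (the quote stops just before the sentence ends): "Safety will be evaluated by comparing the occurrence of AEs and changes in laboratory values of the active treatment arm compared to the active".

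Other safety outcomes have their own tests in the SAP. Symptomatic hypotension, eGFR below 20 and hyperkalemia are Secondary #3 to #5 (logistic regression). All-cause and cardiovascular death are Tertiary #1 and #2 (Cox regression). Protocol 15.9 sends anticipated events to a separate Events of Interest page and keeps them out of AE/SAE capture. The list includes arrhythmia, worsening-HF admission, stroke, syncope, renal events, hyperkalemia, hypotension and angioedema.

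**The concern.** Splitting SAEs by preferred term and reading each p-value against 0.05 can go wrong in two ways. If several terms are common enough to be testable, one of them may cross 0.05 by chance and, under SAP 4, be reported as a significant harm or benefit. If SAEs scatter over many rare terms, a real overall excess may appear only as a list of non-significant lines. In neither case does SAP 13.1 contain one pre-named contrast, with a known error rate, for whether SAEs differed between arms. The tolerability tests do not supply it, because their events are kept out of the SAE data. The death analyses overlap only for fatal SAEs.

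**Working it through.** The documents give no safety power, SAE rate or number of terms, so there is no stated figure on this point to reproduce. As a check of the two-proportion formula, the binary composite in Protocol 16.2 (200 per arm) gives 89.6% for 40% vs 25% (stated 88%) and 55.5% for 40% vs 30% (stated 55%).

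**Inputs.** "Of the 365 patients randomized, 335 will be included in the pre-COVID-19 population" (SAP 3), and "Patients are randomized in a 1:1 ratio to either LCZ696 + Valsartan-placebo or Valsartan + LCZ696-placebo" (SAP 2.2). The actual split is not given; 168 vs 167 is assumed. Two-sided 0.05 comes from SAP 4. Number of terms, term frequencies and independence of terms are assumptions.

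**Step 1: when can a term reach 0.05?** With k affected patients all in one arm, the two-sided mid-p is 2 × ½ × P(all k in that arm), close to 0.5^k. Exact hypergeometric values are 0.061 for k = 4 and 0.030 for k = 5. A term with fewer than 5 patients can never be significant.

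**Step 2: false signals with no true difference.** Size per term is the exact conditional size averaged over Binomial(335, frequency). The family rate for m terms is 1 − (1 − size)^m.

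| Frequency | Size per term | 5 terms | 10 terms | 20 terms |
|---|---|---|---|---|
| 1% | 0.011 | 0.055 | 0.106 | 0.202 |
| 2% | 0.032 | 0.150 | 0.277 | 0.477 |
| 3% | 0.038 | 0.178 | 0.324 | 0.543 |

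For 100 terms at 0.25% the rate is about 1%; for 50 terms at 0.5% it is about 7%.

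**Step 3: a diffuse excess.** Suppose a total SAE frequency of 30% on LCZ696 and 20% on valsartan, spread evenly over m terms.

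| Terms | Per term | P(one term flags harm) | P(any term flags harm) |
|---|---|---|---|
| 10 | 3% vs 2% | 0.065 | 1 − 0.935^10 = 49% |
| 15 | 2% vs 1.33% | 0.041 | 1 − 0.959^15 = 47% |
| 30 | 1% vs 0.67% | 0.0097 | 1 − 0.9903^30 = 25% |
| 60 | 0.5% vs 0.33% | 0.0010 | 1 − 0.9990^60 = 6% |

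One any-SAE comparison of 30% vs 20%: SE = √[(0.30×0.70 + 0.20×0.80)/167.5] = 0.0470; power = Φ(0.10/0.0470 − 1.96) = 57%.

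That 57% takes 30% and 20% as proportions of patients, so it counts each patient once. If the terms are truly independent, some patients have several. With 10 terms the any-SAE proportions are then 1 − 0.97^10 = 26.3% and 1 − 0.98^10 = 18.3%. This gives SE = √[(0.263×0.737 + 0.183×0.817)/167.5] = 0.0453 and power of about 42%.

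**Step 4: like for like.** Simulation, 4,000 trials per scenario. Both analyses use the same simulated patients, and every term's risk is multiplied by 1.5 on LCZ696.

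| Terms (valsartan risk each) | No difference: any term ≤ 0.05 | 1.5-fold: any term flags harm | 1.5-fold: any-SAE test |
|---|---|---|---|
| 100 (0.25%) | 1% | 3% | 48% |
| 50 (0.5%) | 7% | 18% | 46% |
| 25 (1%) | 23% | 47% | 48% |
| 50 (mixed, 0.3–3%) | 29% | 54% | 61% |
| 15 (2%) | 38% | 61% | 54% |

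With many rare terms the excess is usually missed and false signals are few. With fewer, commoner terms the excess is flagged about as often as by one any-SAE test, but with a false-signal rate of 23 to 38%. The any-SAE test holds its false-harm rate near 2.5% throughout.

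**The case against.** Term-level SAE tables with unadjusted p-values are an ordinary safety display, usually read descriptively. SAP 13.1 says the mid-p is to be calculated, whereas the endpoint sections speak of testing significance or comparing statistically. The DSMB reviews safety quarterly and by clinical judgement. A descriptive reading is plausible, but it is not stated, and SAP 4 as written says the opposite. DSMB review does not govern how the final report labels a p-value.

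A reader might infer three stronger points, and the documents do not support them:

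- *That this is the only safety test.* It is not. Hypotension, renal function, hyperkalemia and death each have a pre-named analysis. It is the only planned SAE test.
- *That a chance signal is likely.* Of the nine family rates in Step 2, only one exceeds 50%, and it needs 20 terms at 3% each.
- *That a diffuse excess would be missed.* Setting 4 to 7% power for a single term against 57% for the any-SAE test compares unlike things. Over the whole family, the chance that some term flags harm is near one half with 10 to 15 terms. The any-SAE test would itself miss a 1.5-fold excess 39 to 54% of the time in Step 4.

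The strongest objection concerns the remedy. Because Protocol 15.9 removes the anticipated events, patients with any SAE is a residual count and cannot stand as the lead measure of total serious harm. That objection stands, and the fix has to carry the caveat.

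**Conclusion.** The concern holds for the SAE analysis. As written, SAP 13.1 offers only term-level p-values, exposed to the 0.05 rule of SAP 4, and no controlled overall SAE comparison. The false-signal rate runs from about 1% (100 very rare terms) to about 54% (20 terms at 3%). For a 30% vs 20% excess, the chance that any term flags harm falls from 49% (10 terms) to 25% (30) and 6% (60), against about 57% for one any-SAE comparison, or about 42% if the terms are strictly independent. The two problems do not peak together, so they should not be added up. These sizes rest on an assumed 168 vs 167 split, independent terms, and SAE rates and numbers of terms that the documents do not give. That the overall comparison and the descriptive label are absent rests on the text alone.

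**What to change.** In SAP 13.1:

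1. Add one overall comparison by arm of patients with at least one SAE, with risk difference, 95% CI and p-value. State that it covers only SAEs outside the anticipated-event list in Protocol 15.9.
2. Tabulate the Events of Interest by arm beside it, with risk differences and 95% CIs, so that the SAE line is not read as total serious harm. This also brings the SAP closer to the comparison described in Protocol 18.1.
3. State that the term-level mid-p values are descriptive flags to which the SAP 4 significance rule does not apply.

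Cost: a few sentences, one extra line in the SAE table and one table from the existing Events of Interest page. No new data are needed. The downside is that no single preferred term can then be called statistically significant.

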#### **14. Interim Analyses**

Interim data analysis for efficacy was conducted at the request of the National Heart Lung and Blood Institute (NHLBI). This analysis was performed after 200 patients completed their follow-up and their biomarkers were processed.

Haybittle-Peto methods were used to assess the primary endpoint, using alpha of 0.001, to evaluate whether the trial could be stopped early due to efficacy.

Conditional power was calculated under different scenarios for the primary and secondary endpoints.

Safety data was assessed quarterly by the Data and Safety Monitoring Board (DSMB) based on the reporting of adverse events and otherwise reviewed monthly by the DSMB Chair. There were no pre-specified guidelines for determining stopping rules due to a safety concern; the clinical opinion from the DSMB deliberations will be sole determinant.

#### **15. Subgroup of Interest**

Selected analyses will be performed on the following subgroups: a) patients with and without atrial fibrillation, b) the subgroup of gender will be included to satisfy the NHLBI Inclusion policy, and c) the subgroup of racial or ethnic minority will be included to satisfy the NHLBI Inclusion policy. Models will either adjust for presence of subgroup or will be performed in each subgroup, as appropriate.

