16.2 Sample Size Justification and Randomization

Subjects will be randomized in a 1:1 allocation ratio using a permuted block design with stratification based on the clinical center and atrial fibrillation status. We plan to randomize 400 subjects with planned follow-up of 26 weeks. The primary efficacy endpoint is the proportional change from baseline in the AUC for NT-proBNP levels measured at 2, 4, 8, 12 and 24 weeks.

Based on recent Heart Failure Clinical Research Network (HFN) trials with similar follow-up requirements, we are anticipating a dropout / withdrawal of consent rate of approximately 5%. However, due to deaths and other sample collection issues we anticipate as many as 20-25% of subjects will not have NT-proBNP data at the week 24 assessment.

For the primary analysis, the AUC data will be log transformed and subjects missing the NT-proBNP data at the week 24 assessment will be assigned the last observation carried forward (LOCF). Based on a 2-sample t-test with type I error of 0.05 two-sided, the total sample size of 400 randomized subjects will provide 80% and 90% power to detect a differences of 19% and 21% for LCZ696 compared to valsartan. The PARAMOUNT phase II clinical trial observed a 23% greater reduction in NT-proBNP for LCZ696 compared to valsartan at 12 weeks post-randomization in patient population with HFpEF. ⁶ The HF Network investigators believe a 20% reduction in NT-proBNP would be considered a clinically significant improvement, and this level of change falls within a range considered clinically meaningful in a recent comparative effectiveness review published by AHRQ. ⁷

Sensitivity analyses will examine the influence of the imputation for the informatively missing data. For the complete case analysis, the total sample size of 400 subjects will provide approximately 80% and 95% power to detect reductions of 20% and 25% for LCZ696 compared to valsartan, respectively. These calculations were based on a two-sample t-test and assume that the standard deviation of the log-transformed 180-day AUC measure is 0.70. ⁸

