## 9. Endpoint Descriptions

### 9.1 – Primary Endpoint

**Endpoint Description:** The log of the proportional change from baseline in the area under the curve for the ratio of NT Pro BNP compared to baseline, using the pre-COVID-19 population.

**Response Variable Definition:** All available time points will be used in the calculations. NT Pro BNP is measured at Baseline, Week 2, Week 4, Week 8, Week 12 and Week 24. The ratio of each of the post-Baseline measures will be calculated versus Baseline. The area under the entire piecewise dataset is the response variable. A visual example is provided showing a patients' hypothetical data for NT Pro BNP ratio to Baseline.

This area is determined by calculating the sum of the areas of each of the individual trapezoids. Each trapezoidal area is composed of the area bordered by the time interval on the x-axis (e.g., 0 to 2 Weeks), the respective NT Pro BNP ratio at each of the time points on the y-axis (e.g., 1 at x=0 and 0.7 at x=2), and the line segment connecting the NT Pro BNP ratios between the two y-axis values (1 and 0.7). The number of trapezoids available will depend on the completeness of the data.

It is expected that NT Pro BNP measurements may not be measured exactly at the specified time points. For example, the measurement corresponding to the 12 Week time point may actually be measured for example at 11 or 12.5 Weeks after randomization. In calculating the AUC, the measurement corresponding to Baseline will always be set at the 0 time point. Each post-Baseline visit will use the value for the visit timing, even if that timing is not exact (e.g., Week 12 visit will always assign a 12 for the x-axis). The final step in the calculation is to take log of the calculated area under the curve.

Additional Covariates in Addition to Randomized Treatment: Baseline log NT Pro BNP, atrial fibrillation status, random effect of patient

Handling of Dropouts and Missing Data: If missing NT Pro BNP at Week 24, use last observation carried forward (LOCF) from previous post-Baseline time point with available NT Pro BNP data. No adjustment will be made for missing Baseline results.

Sensitivity Analysis: Several sensitivity analyses will be performed.

- 1) Complete cases, using patients with available Baseline and Week 24 Week 24 NT Pro BNP data
- 2) For patients missing Week 24 value, impute 2.5xBaseline value for Week 24

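### The SAP's two subgroup methods (adjust for the subgroup, or fit separate models) do not test whether the treatment effect differs, so chance discordance in significance can be misread as effect modification

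*SAP*

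**What the plan says.** SAP section 15 is the whole subgroup plan. It opens with "Selected analyses will be performed on the following subgroups" and does not say which endpoints are meant. It lists three factors: "a) patients with and without atrial fibrillation, b) the subgroup of gender will be included to satisfy the NHLBI Inclusion policy", and racial or ethnic minority status, which is also there for that policy. It then gives the method: "Models will either adjust for presence of subgroup or will be performed in each subgroup, as appropriate".

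Three other places bear on the point.

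- SAP section 9.1 lists the covariates of the primary model besides treatment: "Baseline log NT Pro BNP, atrial fibrillation status, random effect of patient". AF status is therefore already a main effect.
- The significance rule is general. Protocol section 16.1 states "Statistical tests with a 2-sided p-value <0.05 will be considered statistically significant, unless otherwise stated". SAP section 4 applies a 0.05 threshold to all endpoints and adds that "all tests will be 2-sided". Neither document exempts subgroup results or gives a rule for reading them.
- No endpoint description in SAP sections 9 to 13, and nothing in Protocol section 16, includes a treatment-by-subgroup interaction or any other test of heterogeneity.

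**The concern.** A subgroup analysis asks whether the treatment effect differs between levels of a factor. Neither named option answers that.

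- **Adjusting for the subgroup** adds a main effect. It allows the outcome to differ between, say, men and women, but forces the treatment effect to be the same in both. For AF it adds nothing, since the term is already in the primary model.
- **Fitting the model in each subgroup** gives two estimates and two p-values, but no planned comparison between them. With a general 0.05 rule in force, the natural reading is that one level is significant and the other is not. That pattern depends heavily on subgroup size and chance, and is poor evidence that the effects differ.

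What is at stake is interpretation: an apparent difference by AF, sex or minority status that the data do not support.

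**Working it through.** **Inputs from the documents**

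- SD: Protocol section 16.2 assumes "the standard deviation of the log-transformed 180-day AUC measure is 0.70".
- Reference effect: the same section says the investigators "believe a 20% reduction in NT-proBNP would be considered a clinically significant improvement". On the log scale, d = −ln(0.80) = 0.2231.
- N = 335, the pre-COVID-19 population (SAP section 3).
- 1:1 allocation (SAP section 2.2) and two-sided α of 0.05.

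**Inputs assumed.** The documents do not give the subgroup shares f. I use 20–50%. I also assume 1:1 balance within each level, normal theory, and all 335 patients contributing.

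**Step 1: reproduce the plan's own figure.** Protocol section 16.2 gives complete-case power of about 80% and 95% for reductions of 20% and 25%, with 20–25% of week 24 values missing. That leaves 150–160 of 200 per arm. Power = Φ(d/SE − 1.96) + Φ(−d/SE − 1.96), with SE = 0.70·√(2/n).

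- 20% reduction: 78.8% (n = 150) to 81.4% (n = 160).
- 25% reduction: 94.5% to 95.7%.

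The stated figures reproduce, so the SD of 0.70 is used as the plan uses it.

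**Step 2: chance that exactly one level is significant when the true effect is identical in both.** In a level with share f, SE = 0.70·√(4/(335·f)). With powers p₁ and p₂ in the two levels, the probability is p₁(1 − p₂) + p₂(1 − p₁).

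Example with a 40/60 split (134 and 201 patients) and a 20% reduction:

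- SE₁ = 0.70·√(4/134) = 0.121, so p₁ = 0.454.
- SE₂ = 0.70·√(4/201) = 0.099, so p₂ = 0.618.
- Probability = 0.454 × 0.382 + 0.618 × 0.546 = 0.51.

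| True reduction in both levels | Exactly one level significant (shares 30–50%) |
|---|---|
| 0% | about 10% (2 × 0.05 × 0.95 = 9.5%) |
| 10% | about 28% |
| 15% | 44–46% |
| 20% | 50–55% |
| 25% | 37–47% |
| 30% | 17–29% |

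A more uneven 20/80 split gives 62% at a 20% reduction.

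**Step 3: three factors together.** I simulated three independent factors with assumed shares of 40%, 27% and 40%. At least one factor is discordant in about 79% of trials at a uniform 20% reduction, 46–47% at 10%, and 21–22% with no effect. Other sets of shares give about 75–85% at 20%.

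**Step 4: what an interaction test would do.** Its standard error is √(SE₁² + SE₂²). For the 40/60 split this is √(0.121² + 0.099²) = 0.156.

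- False-positive rate: 5% per factor, and about 1 − 0.95³ = 14% for at least one of three. Under a uniform 20% effect, it would be significant in only about 6–10% of the discordant results in Step 2.
- Power for a 20% reduction in one level and none in the other: at 40/60, 0.2231/0.156 = 1.43, giving 30%. Across shares of 20–50% it is about 21–31%.
- The ratio of effects detectable with 80% power is about 0.59–0.65.

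**The case against.** The strongest reply is that section 15 makes no claim about effect modification. It does not say that p-values will be compared across levels, and two of the three factors are there to meet a funder's inclusion policy. Separate fits also yield estimates, and Protocol section 16.4 reports the primary treatment effect with a point estimate and 95% CI, so a careful reader could form the contrast unaided. This stands in part: misreading is a risk, not something the plan sets out to do. But the contrast is not planned, and the general 0.05 rule is not switched off for subgroups. One might also argue that adjusting was meant to include an interaction term. The text does not say so.

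A reader might infer that discordance will occur, that it is the normal result under a uniform effect, or that false claims by sex or race will follow. The documents do not support that. Per factor, the chance is about even at a 20% reduction, which is close to the worst case. It is much lower at 10% or 30%, and it depends on shares the documents do not give.

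It is also fair to object that an interaction test is weak at this sample size. That is right. It is why the interval should be reported and a non-significant result not read as uniformity. Low power does not make two within-level p-values a better guide.

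**Conclusion.** The concern holds as a gap in method. Neither option in SAP section 15 shows whether the treatment effect differs by AF, sex or minority status, and for AF the adjusting option duplicates the primary model. Chance discordance can then be misread as effect modification. Its size varies with the true effect: per factor, from about 10% of trials with no effect to a peak of about half at a 20% reduction, and lower again for larger effects.

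These figures rest on the protocol's SD, on 335 contributing patients and on assumed shares. The three-factor figures also assume independent factors. If baseline adjustment lowers the residual SD, each figure moves as it would for a larger true effect.

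The subgroups carry no alpha and do not enter the primary or key secondary conclusion, so the validity of the primary test is not in question. The change is worth making because it is cheap, but it is not critical.

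**What to change.** Replace the method sentence in SAP section 15 with text to this effect:

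- For the primary and key secondary endpoints, the endpoint's own model will include treatment, subgroup and treatment-by-subgroup terms, one factor at a time. For AF in the primary model, only the interaction term is new.
- For the key secondary endpoint, the inverse-probability weighting of section 10.1 is kept, and the SAP states how the censoring weights are estimated (for example by arm, or by arm within subgroup).
- The interaction estimate, its 95% CI and its p-value are reported beside subgroup-specific estimates with 95% CIs.
- The results are labelled exploratory, and no significance claim is made within a subgroup.
- A non-significant interaction is not evidence of a uniform effect, given power of about 21–31% for a 20% reduction in one level and none in the other.

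The cost is a short paragraph, one extra model term per factor, and a decision on the weights for the key secondary endpoint. No new data are needed. The drawback is slightly more analysis work and an interaction test that will often be inconclusive.
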